5.5 Criterion for Response

Response is defined as follows:

Complete response is defined as no endometrial abnormality or the presence of endometrial hyperplasia without cytologic atypia at the one year time point.

Partial response is defined as the presence of complex endometrial hyperplasia with cytologic atypia in patients with an initial diagnosis of grade 1 endometrial cancer, at the one year time point.

Stable disease is defined as no change in diagnosis at the one year time point.

Progressive disease is the presence of grade 2 cancer or above in patients with an initial diagnosis of grade 1 cancer OR presence of grade 1 cancer or above in patients with an initial diagnosis of complex atypical hyperplasia at any time point.

Patients with stable disease or progressive disease will be categorized as non-responders for the purposes of molecular analysis.

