5.8 Long-term Follow-up

All patients will be followed for 5 years from their last study-specific intervention, unless consent is withdrawn or the patient is lost to follow-up. No clinic visits or other patient contact is required for follow-up. Patient survival, disease status, and fertility outcomes will be followed annually through review of their medical record.

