We will calculate period prevalence and incidence of recurrence along with 95% confidence intervals. Period prevalence is calculated as the number of patients who recur divided by number of patients at risk for recurrence. Incidence is calculated as the number of patients who recur divided by person-time follow-up. Recurrence is defined as return to original disease state or worse after being disease-free. Finally, the proportion of patients who return to a worsening disease state after an initial response will be calculated. Specifically, it will calculate the proportion of patients who have progressive disease if their best response was stable disease, partial response, or complete response.

Summary statistics will be calculated for disease status and fertility outcomes. This analysis will be descriptive.

We will calculate period prevalence and incidence of recurrence along with 95% confidence intervals. Period prevalence is calculated as the number of patients who recur divided by number of patients at risk for recurrence. Incidence is calculated as the number of patients who recur divided by person-time follow-up. Recurrence is defined as return to original disease state or worse after being disease-free. Finally, the proportion of patients who return to a worsening disease state after an initial response will be calculated. Specifically, it will calculate the proportion of patients who have progressive disease if their best response was stable disease, partial response, or complete response.

Summary statistics will be calculated for disease status and fertility outcomes. This analysis will be descriptive.

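### Both loss-of-response measures in section 7.5 miss the same two relapse paths in patients who enter with grade 1 cancer

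*Combined protocol and SAP*

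**What the plan says.** Section 7.5 plans two summaries of what happens after a response.

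- **Recurrence.** "We will calculate period prevalence and incidence of recurrence along with 95% confidence intervals". The event is given as: "Recurrence is defined as return to original disease state or worse after being disease-free". The two statistics are: "Period prevalence is calculated as the number of patients who recur divided by number of patients at risk for recurrence"; and "Incidence is calculated as the number of patients who recur divided by person-time follow-up".
- **Worsening after response.** This is announced broadly: "the proportion of patients who return to a worsening disease state after an initial response will be calculated". The next sentence specifies it as "the proportion of patients who have progressive disease if their best response was stable disease, partial response, or complete response".

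Section 7.5 also promises a descriptive summary of disease status.

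The terms come from section 5.5. Complete response means a normal endometrium or hyperplasia without atypia. "Partial response is defined as the presence of complex endometrial hyperplasia with cytologic atypia in patients with an initial diagnosis of grade 1 endometrial cancer", judged at one year. Progressive disease means grade 2 or higher for a patient who entered with G1 EEC, and grade 1 cancer or higher for one who entered with CAH. Section 7.3 counts both complete and partial response as success in the primary outcome.

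On follow-up, section 5.8 states: "All patients will be followed for 5 years from their last study-specific intervention". This is done by annual chart review with no required visit. Section 5.7 lists hysterectomy as one of three options for patients who complete the year.

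**The concern.** The recurrence definition sets two conditions: the patient must have been disease-free, and must then reach at least her entry diagnosis. The second measure looks designed to catch what recurrence leaves out, but its specification narrows it to progressive disease, which for a G1 EEC entrant starts at grade 2. Between the two lies a gap in which a G1 EEC entrant can get worse without being counted.

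The consequence is an asymmetry between the primary outcome and the follow-up of it. A woman who goes from G1 EEC to CAH is a responder in the headline result. If she then goes back to G1 EEC, neither measure records that the response was lost. Section 2.2 describes G1 EEC as the less well studied of the two indications, so the long-term summary is weakest where information is scarcest.

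A second, smaller issue sits in the same paragraph. The incidence denominator has no start, no stop and no restriction to patients at risk, whereas the prevalence denominator is limited to those at risk.

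**Working it through.** **No figure to reproduce.** The documents state no expected recurrence rate, number of events or precision for these summaries. The check is therefore a complete listing of cases under the plan's own rules.

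**Rules.** Order the states as disease-free < CAH < G1 EEC < grade 2 or higher. For entry diagnosis E, best state B and later state L:

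- worsening: L > B
- recurrence (7.5): B is disease-free and L ≥ E
- progressive disease (5.5): L > E

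A complete response is treated here as disease-free, which 7.5 does not actually say.

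| Entry | Best state | Later state | Recurrence | Progressive disease |
|---|---|---|---|---|
| CAH | disease-free | CAH | yes | no |
| CAH | disease-free | G1 EEC | yes | yes |
| CAH | disease-free | grade 2+ | yes | yes |
| CAH | CAH | G1 EEC | no | yes |
| CAH | CAH | grade 2+ | no | yes |
| G1 EEC | disease-free | CAH | **no** | **no** |
| G1 EEC | disease-free | G1 EEC | yes | no |
| G1 EEC | disease-free | grade 2+ | yes | yes |
| G1 EEC | CAH | G1 EEC | **no** | **no** |
| G1 EEC | CAH | grade 2+ | no | yes |
| G1 EEC | G1 EEC | grade 2+ | no | yes |

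Nine of the 11 paths are caught by at least one measure. The two that are not both belong to G1 EEC entrants. All five CAH-entry paths are caught.

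**Effect on the counts (assumed numbers).** Suppose 10 G1 EEC entrants reach complete response and 3 relapse, 2 as CAH and 1 as G1 EEC. The plan reports 1/10 = 10%; the share who lost complete response is 3/10 = 30%. For partial responders who return to G1 EEC and go no further, the two measures count zero, however many there are.

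**Person-time (assumed numbers).** Take a constant hazard λ, five years of follow-up, and a share h whose hysterectomy at time t removes all risk. Per patient:

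- time at risk R = (1 − h)(1 − e^(−5λ))/λ + h(1 − e^(−λt))/λ
- time if the clock keeps running = R + h·e^(−λt)·(5 − t)
- ratio of computed rate to at-risk rate = R / (R + h·e^(−λt)·(5 − t))

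Example with λ = 0.10, h = 0.25, t = 1: R = 0.75 × 3.935 + 0.25 × 0.952 = 3.189; added time = 0.25 × 0.905 × 4 = 0.905; ratio = 3.189/4.094 = 0.78.

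| Share with hysterectomy | At about time 0 (λ 0.05 to 0.20) | At 1 year (λ 0.05 to 0.20) |
|---|---|---|
| 0% | 1.00 | 1.00 |
| 10% | 0.85 to 0.89 | 0.90 to 0.92 |
| 25% | 0.66 to 0.73 | 0.76 to 0.79 |
| 50% | 0.39 to 0.47 | 0.55 to 0.59 |

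If the clock stops at hysterectomy, the ratio is 1.00 throughout. The same silence covers patients who were never disease-free. With λ = 0.10 and an assumed 35% of such patients each adding five years, the ratio is 0.65 × 3.935 / (0.65 × 3.935 + 0.35 × 5) = 2.558/4.308 = 0.59.

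**The case against.** The strongest defence is that recurrence ordinarily presupposes a disease-free interval, so leaving partial responders out of it is normal usage. That stands. The defect for them lies in the companion measure, which is announced as worsening after response and then restricted to progression.

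It can also be said that 5.5 classifies status at one year and defines no loss of response, and that CAH in a G1 EEC entrant is itself a partial response and hence a success. On that view, moving from complete response to CAH is a step between two grades of success. That is a coherent endpoint. But 5.5 excludes atypia from complete response, so such a patient no longer meets the category she was placed in, and a summary of what happens after response should show it.

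Three further limits stand. The missed patients could still appear in the descriptive disease-status summary, so it would be wrong to say they are counted nowhere. These are secondary estimates with no test or decision rule attached. Objective 1.2.4 names survival, disease status and fertility without ranking them, and does not name durability of response.

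A reader might infer from the five-year follow-up in 5.8 that the incidence rate counts time after hysterectomy. The documents do not say so. Section 5.8 sets how long charts are reviewed, not a rate denominator. Section 5.7 offers hysterectomy only to patients who complete the year and only as one of three options, and no expected uptake is given. The supportable statement is that person-time is undefined.

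**Conclusion.** The point holds for G1 EEC entrants. Two worsening paths fall outside both measures by the plan's own wording, so loss of response is understated whenever either path occurs. A missed patient enters the counts only if she worsens further: to G1 EEC after a complete response, or to grade 2 or higher after a partial one.

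The size cannot be derived, because the documents give no relapse rate, G1 EEC share or split of relapses by histology. The 10% against 30% example shows the mechanism and is not a forecast.

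CAH entrants are unaffected, provided a complete response counts as disease-free. If hyperplasia without atypia were held not to be disease-free, a CAH entrant who responded that way and returned to CAH would be missed too.

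A firm claim that the incidence rate is biased by post-hysterectomy time is not supported. On assumed inputs the ratio to the at-risk rate runs from 1.00 down to 0.39, depending on how the undefined term is read and on unknown uptake and timing. If the clock does run on, the dilution is downward, the same direction as the omissions.

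The primary endpoint, the futility rule and the sample size are untouched.

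**What to change.** Amend section 7.5 as follows. The recurrence paragraph is printed twice there, and both copies need the change.

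1. Add a secondary loss-of-response measure: CAH or worse after complete response in either cohort, or G1 EEC or worse after partial response. This replaces the restriction of the worsening measure to progressive disease. Report it by entry diagnosis.
2. Keep the current recurrence definition and report it alongside, stating whether every complete response counts as disease-free.
3. Define incidence person-time as time at risk in patients with a documented response, from that response to the earliest of the event, hysterectomy, death or last assessment on the chart.

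A competing-risk display with hysterectomy as the competing event would be a reasonable extra, but it is a preference and not needed to close the gap.

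The cost is SAP wording and a small amount of analysis, since disease status is already reviewed annually under 5.8. There are three downsides. The reported loss-of-response figure will be higher. Assessment dates depend on what the chart holds, because no visits are required after the first year. The partial-response component rests on telling CAH from G1 EEC, which section 2.1 describes as difficult; for G1 EEC entrants in complete response, the new measure no longer depends on that distinction, whereas the current recurrence definition does.

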8.0 Data and Protocol Management

This study is planned as a multi-site study. All patients will be centrally registered into the Clinical Oncology Research System (CORe) at M. D. Anderson Cancer Center. Information will include a completed eligibility check list, patient name, date of birth, consent date, and race. Once accrual is complete, study data will be combined for analysis.

Protocol Compliance: The study research nurse will be present at each visit to ensure compliance with protocol guidelines. Decisions for removal from study based on response will be made by the Study Chairman and the Study Pathologist ([name]).

Data Entry: Data must be entered into the Gyn Oncology Departmental database for this protocol.

Accuracy of Data Collection: The Study Chairman will be the final arbiter of response or toxicity should a difference of opinion exist.

9.0 Adverse Event Reporting

9.1 Reporting Adverse Events

All **Internal** and **External** AEs that include all of the following will be promptly reported to IRB via the Office of Protocol Research (OPR):

- Serious
- Unexpected
- Related (definitely, probably, or possibly related) to participation in the research.

Timeline for prompt reporting of Internal AEs:

1. **Within 1 working day (24 hours) from the time the research team becomes aware of the event** = All deaths that occur during treatment and within 30 days after completion of treatment.
2. **Within 5 working days from the time the research team becomes aware of the event** = All serious, unexpected and related AEs other than those deaths described above in number 1.

Internal SAEs will be reported from the time protocol specific consent is signed, and screening or treatment has begun, during the course of treatment and within 30 days after the last day of active treatment.

Beyond 30 days of treatment, completion of only those SAEs that, in the judgment of the investigator, are related to research will be reported.

Reporting Timeline for prompt reporting of External AEs:

1. **Within 5 working days from the time the research team becomes aware of the event** = All related deaths that occur during treatment and within 30 days after completion of treatment.
2. **Within 5 working days from the time the research team becomes aware of the event** = All serious, unexpected and related AEs other than those deaths described above in number 1.

External SAEs will be reported to the IRB beginning on the date of the UTMDACC IRB approval letter of the associated protocol.

SAEs Requiring Documentation on AE Log:

All SAEs that do not fall under the prompt reporting requirements will be reported during continuing review using the **Internal** or **External** SAE Log or database printout.

Note: If a trend or recurring adverse events are seen, the PI will report these events using the **Internal** or **External** SAE report Form for prompt reporting.

These reporting guidelines do not affect the reporting requirements to the FDA, the sponsor or monitoring agency.

Reporting for trials involving minimal risk

For protocols designated as minimal risk, AEs considered serious, unexpected and definitely, probably or possibly related to the study will be reported promptly as described above. [AEs considered to be unrelated to the study and non-serious AEs will be reported during continuing review (annual report)].

Reporting of SAEs for Terminated Protocols

Only those serious AEs that were unexpected and may impact the health, welfare or safety of subjects will be reported. For example, reports of secondary malignancies or problems with implanted devices.

DEFINITIONS

Adverse Event (AE) – Any untoward or unfavorable medical occurrence in a human subject, including any abnormal sign (for example, abnormal physical exam or laboratory finding), symptom, or disease, temporally associated with the subject's participation in the research, whether or not considered related to the subject's participation in the research.

For minimal risk studies such as behavioral science, laboratory, and epidemiologic protocols, as well as chart reviews, reasonable judgment must be used to determine what constitutes an AE.

Expected AE - Any AE with specificity or severity that is consistent with the current Investigator Brochure (IB) or consistent with the risk information described in the Informed Consent Document (ICD) or general investigational plan. All clinical protocols should include a list of the expected and anticipated events or hospitalizations relating to the study treatment.

Unexpected (Unanticipated) AE - Any AE, with specificity or severity that is not consistent with the current IB or not consistent with the risk information described in the ICD or general investigational plan.

Serious Adverse Event (SAE) – Any AE associated with the subject's participation in research that:

- results in death;
- is life-threatening, (places the subject at immediate risk of death from the event as it occurred);
- results in inpatient hospitalization or prolongation of existing hospitalization;
- results in persistent or significant disability/incapacity;
- results in a congenital anomaly/birth defect; or
- based upon appropriate medical judgment, may jeopardize the subject's health and may require medical or surgical intervention to prevent one of the other outcomes listed in this definition.

Internal AE - An AE occurring in a subject who is enrolled in a protocol or study that is under the oversight of a UTMDACC IRB.

External AE – An AE occurring in a subject who is not enrolled in a UTMDACC protocol or is on a protocol at a site that is under the oversight of another IRB. Generally, the PI has received notification of this AE from the protocol sponsor. Example: Medwatch report, CIOMS report, Safety reports.

Related:

Events directly or indirectly attributed to study drug, device or procedures and/or study participation. Events occurring with sufficient frequency to suggest that they are not random.

Unrelated:

Events that would occur regardless of study participation, including events that are clearly random occurrences. If the frequency of the event suggests a possible connection to the study

intervention, then it should be considered related.

AE Attribution - The determination of whether an AE is related to the research (medical treatment or intervention):

Definite – It is clearly related
Probable - It is likely related
Possible - It may be related
Unlikely - It is doubtfully related
Unrelated - It is clearly NOT related

AE Severity - Refers to the intensity (grading) of a specific AE. All clinical trials conducted at UTMDACC must use the “CTCAE v3.0 grading scale” for AE documentation and reporting (Publish date June 10, 2003). For the purpose of this policy, toxicity is synonymous with AE.

Minimal Risk - Minimal risk means that the probability and magnitude of harm or discomfort anticipated in the research are not greater than those ordinarily encountered in daily life or during the performance of a routine physical examination, physiological examination or laboratory testing.

Designation of minimal risk will be determined by the IRB at the time of initial approval and reviewed at least annually during continuing review.

Multicenter Studies

Since UTMDACC PIs participating in multicenter trials are unable to prepare a meaningful summary of SAEs, at the time of continuing review they should submit the current report from the monitoring entity (e.g. research sponsor, coordinating statistical centre, or DSMB/DMC). The report should include the following:

- a statement as to what information was reviewed by the monitoring entity (e.g. study-wide AEs, interim findings, recent literature relevant to the research);
- date of the review;
- monitoring entity's assessment of the information. Information that is considered inadequate by the PI should be returned to the monitoring agency/sponsor for completion

9.2 Eliciting Adverse Event Information

Adverse events will be elicited at each clinic visit during participation in the study. Patients will be given a worksheet to record the occurrence of adverse events throughout the study. All adverse events which are directly observed and all adverse events which are spontaneously reported by the patient are to be documented by the investigator.

9.3 Grading/Rating Scale

All adverse events reported during the study will be evaluated and graded on a scale of 1-4.

Grade	Rating	Description
1	Mild	Adverse event is transient and easily tolerated by the patient; asymptomatic
2	Moderate	Adverse event causes the patient discomfort and interrupts the patient's usual activities; symptomatic but does not interfere with function
3	Severe	Adverse event causes considerable interference with the patient's usual activities
4	Life-Threatening	Adverse event is incapacitating or life-threatening

10.0 Data Confidentiality Plan

On enrollment, patients will be assigned a study number. All study documents will be de-identified of any patient information such as name, social security number, date of birth, or medical record number. Data collection files will be stored in a locked file cabinet. The document which links the identifiable patient information to a study number will be stored in a password-protected computer file. Once the data have been analyzed, all identifiers will be destroyed.

